The longstanding view has been that insomnia, and other forms of sleep disturbance, emerge as a consequence of dementia and are the result of progressive neuronal damage. However, there is growing evidence that the direction of causation may go both ways, with sleep disturbance potentially increasing vulnerability to dementia. Longitudinal studies have found that sleep disturbance often precedes and increases risk for dementia by several years. The purpose of this study is to examine the relationship

between chronic insomnia and dementia biomarkers and orexin levels found in cerebrospinal fluid (CSF). Fifteen adults age 30-50 with chronic insomnia and age- and gender-matched good sleepers will undergo overnight polysomnography and CSF sampling in the morning.

Objectives

Overall objectives

Patients with dementia very frequently have disturbed sleep that is thought to be caused, in part, by the dementing illness. There is growing evidence of the reverse direction of causation, with sleep disturbance increasing vulnerability to dementia. The recently-discovered glymphatic system, by which waste from neural metabolism is cleared from the brain, may be a mechanism for the sleep-dementia link. The goal of this project is to examine the relationship between chronic sleep disturbance (insomnia) and dementia biomarkers and orexin levels as assessed in cerebrospinal fluid (CSF). Fifteen adults age 30-50 with chronic insomnia and age- and gender-matched good sleepers will undergo overnight polysomnography and morning CSF sampling. These data will be used to address the following specific aims: Specific Aim 1: To examine the association between chronic insomnia and CSF markers of dementia. Hypothesis 1: Chronic insomnia will be associated with higher levels of CSF AB markers compared to good sleepers. Specific Aim 2 (exploratory): To examine the role of orexin in mediating the relationship between chronic insomnia and CSF markers of dementia. Hypothesis 2: Higher CSF orexin levels will mediate the relationship between chronic insomnia and A markers.

Primary outcome variable(s)

Dementia biomarkers in cerebrospinal fluid

Secondary outcome variable(s)

CSF orexin levels

Background

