Participants will be recruited through targeted advertisements in the Philadelphia area community. We have a track record of success in recruitment through these approaches. To estimate the appropriate sample sizes, statistical calculations were carried out using pilot data obtained from OxA and ABO measurements from N=6 individuals. Specifically, two-sided two-sample t-test was utilized for a two-group parallel design study which compared chronic insomniacs with good sleepers. For OxA, sample sizes needed to detect intended effect sizes (differences of 30%, 40%, and 50) were estimated at 80% power. For ABO, sample sizes were calculated to significantly detect the differences between two groups of 50%, 100%, and 150% at 80% power. Power calculations were performed on OxA and ABO in raw and natural log scales, respectively, after examining the normality of data with residual plots. Variability estimates at each time point were obtained as averages of sample standard deviations of two treatment groups per time point. As such, N=15/group would be sufficient to identify changes in the 8 AM samples considering effect sizes equal or greater than 30% and 100% for OxA and ABO, respectively.

Key inclusion criteria

All subjects must meet the following criteria: -Age 30-60 -Men and women To be included in the insomnia group, subjects must meet the following DSM5 Diagnostic Criteria for insomnia disorder: - dissatisfaction with sleep quantity or quality (difficulty initiating or maintaining sleep, or waking up too early) despite adequate opportunity for sleep -sleep disturbance causes clinical significant distress or impairment in functioning -present at least 3 times per week for at least 3 months -sleep disturbance is

not better explained by a medical or psychiatric condition or based on the effects of a substance - Insomnia Severity Index (ISI) score 14 or greater.

Key exclusion criteria

-Diagnosis or evidence of sleep disorders other than insomnia as determined by the screening questionnaires and clinical history -Women who have been pregnant or lactating within the past six months -Non-fluency in spoken or written English -Current or past month shiftwork defined as working during the evening or night shift -Current use of medications or OTC products that impact sleep - Evidence of neurological abnormalities that could include the risks associated with lumbar puncture (e.g.papilledema, mass lesion, Chiari malformation).

Vulnerable Populations

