
lateral to the outer canthus of the left eye and 1 cm above and lateral to the outer canthus of the right eve. Two surface EMG electrodes will be taped onto the chin 2 cm apart. Additional leads will be used to measure leg movements and breathing in order to rule out the presence of occult sleep disorders. Two electrodes will be taped over the anterior tibialis muscle of each leg to detect leg movements during the night. Flexible Resp-EZ belts will be placed around the abdomen and chest to measure breathingrelated movements during the night. A nasal cannula will be used to detect pressure and an oximeter probe will be placed on the finger to measure blood oxygen saturation. Records will be scored in 30second epochs according to standard criteria. PSG data will be used to compute standard sleep architecture variables of the amount of each stage of sleep in terms of minutes and percentage of total sleep time. In addition the following sleep continuity variables will be computed: sleep latency (SL: time from lights out to the first epoch of stage 2 or higher), total sleep time (TST), wake after sleep onset (WASO; number of minutes spent awake between lights out and lights on), and sleep efficiency (SE; total sleep time divided by the total recording period). Additionally, our technicians will attached two sensors to the chest area of the subjects in order to measure respiration and test the sensors to see the accuracy of detecting sleep apnea. TatchSleep is a flexible, thin, and wireless adhesive patch designed to collect physiological parameters related to sleep disorders in patients. Each patch consists of a wearable sensor and a bottom layer of double coat medical-grade adhesive. This adhesive is safe for patient use and enables the patch to stay affixed to the body throughout the night. The sensor also connects directly to a battery which is hidden within the patch. During the study, patients will be asked to wear three patches. Data from the patches are transmitted wirelessly throughout the night to a companion mobile application, which stores the data for clinicians to upload to a sleep analysis platform. Upon waking, wires will be removed and the subjects will be allowed to shower. Those in the insomnia group who choose to participate in the optional second part of the protocol will have a fasted blood draw at this visit. Study staff will walk the subjects over to CHPS outpatient. Around 8:00 AM a lumbar puncture will be performed by a neurology fellow to collect 25 mL of CSF. Prior to the lumbar puncture the neurology fellow will conduct a neurological exam including fundoscopic exam, in order to rule out any contraindications to the procedure such as a coagulopathy or central mass lesion. If contraindications are found, the lumbar puncture will not be performed and the subject will be withdrawn from all further study procedures. If no contraindications are found, a small, specialized needle called a sprotte needle will introduced through an introducer. This type of needle has been demonstrated to reduce risk of headache. 25 mL of CSF will be collected and stored in polypropylene transfer tubes. In addition, bedrest for one or more hours immediately after the procedure will be recommended to the participant. Oral hydration will be encouraged to help reduce risk of headache. After final samples are taken participants will have completed the protocol and will be free to leave. CSF Analysis: Analysis 1: Endogenous ABO levels in human CSF will be measured in a blind fashion in a flow-based ABO-specific sandwich ELISA using the Erenna immunoassay system (Millipore, Temecula, CA), described in Savage et al 2014 JN. In brief, Mercks proprietary 19.3 antibody coupled to paramagnetic microparticles will be used to capture ABO, repeatedly washed with assay-specific proprietary buffers, and detected using a fluor-labeled detection antibody, 82E1 (IBL, Minneapolis, MN). Human CSF samples (100 uL/well) will be loaded in a blinded fashion in triplicate. The standards (ADDL), prepared in-house, will be run alongside CSF samples in triplicate using a 12-point ¹/₂ serial dilution between 42 pg/mL and 0.04 pg/mL. Statistical analysis of the data, including limit of detection (LOD) for the assay (defined as 2 x SD Bkg/slope with percent coefficient of variance 20%) and unknown ABO concentrations will be calculated using Singulex Sgx link and GraphPad Prism (GraphPad Software, Inc., San Diego, CA) software. Analysis 2: OxA concentrations in CSF will be quantified by an in-house ELISA developed using Meso Scale Discovery (MSD) electrochemiluminescence detection technology platform (Gaithersburg, MD, USA). Purified polyclonal IgG (G-003-36, Phoenix Peptide, Burlingame, CA, USA), raised in rabbit against OxA (amino acids 16-33), will be used as a capture antibody. Goat anti-human polyclonal antibody against OxA (N-18) (sc-26491, Santa Cruz Biotechnology Inc., Santa Cruz, CA, USA) will be used as a primary detection antibody. Sulfo-Tag labeled anti-goat antibody, raised in donkey, will be used as a secondary detection antibody and will be provided by MSD (R32AG-5). Blinded CSF samples will be run in triplicate alongside OxA standard (run as a 10-point 1/3 serial dilution between 30,000 and 4.57 pg/mL). Statistical analysis of the data, including lowest detection limit (LDL) for the assay (defined as 2 x SD Bkg/slope with percent coefficient of variance 20%) and unknown OxA concentrations will be calculated by extrapolating a nonlinear regression curve (sigmoidal, 4PL, X is log (Concentration)) and will be corrected for weight by 1/Y² using GraphPad Prism (GraphPad Software, Inc., San Diego, CA) software.

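### WASO is counted from lights out, so as written it is total wake time, not wake after sleep onset: a minor correction to a descriptive sleep variable

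*Combined protocol and SAP*

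**What the plan says.** The combined protocol and SAP, under Study Procedures, Procedures, lists the variables to be derived from the overnight polysomnogram. After sleep architecture it says "In addition the following sleep continuity variables will be computed" and gives four: sleep latency, total sleep time, WASO and sleep efficiency. Three carry their own rule:

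- "sleep latency (SL: time from lights out to the first epoch of stage 2 or higher"
- "wake after sleep onset (WASO; number of minutes spent awake between lights out and lights on"
- "sleep efficiency (SE; total sleep time divided by the total recording period"

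Records are scored in 30-second epochs. No other section narrows or replaces the WASO rule. The total recording period in the efficiency rule is not defined further.

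**The concern.** The name says that counting starts at sleep onset. The rule starts it at lights out, which is where sleep latency also starts. Minutes awake before sleep onset therefore enter both variables, and the quantity labelled WASO is all wake in the lights-out-to-lights-on interval.

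At stake is the description of sleep on the night before the lumbar puncture. A value reported as WASO but computed this way is not comparable with WASO counted from onset. It also mixes difficulty falling asleep with difficulty staying asleep. Under Key inclusion criteria, the insomnia group may qualify through "difficulty initiating or maintaining sleep, or waking up too early", so pre-onset wake may well differ between the groups. A descriptive difference in WASO would then be partly a difference in latency.

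**Working it through.** The documents state no WASO or latency figure, so there is nothing to reproduce. The check is epoch accounting.

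**Inputs from Procedures.** The WASO window is lights out to lights on. Sleep latency (SL) is "time from lights out to the first epoch of stage 2 or higher". Sleep efficiency (SE) is "total sleep time divided by the total recording period". The scoring unit is 0.5 minutes.

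**Notation, in minutes.** P is wake before onset, N is stage 1 before the first stage 2 epoch, S is sleep from onset on, and W is wake from onset to lights on. The interval T from lights out to lights on is P + N + S + W.

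**Formulas.**

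- SL = P + N
- Total sleep time (TST) = N + S
- WASO as written = P + W = T − TST
- Wake after onset = W
- Excess = (P + W) − W = P

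Only the wake part of SL is absorbed. The stage 1 minutes N belong to SL but are not wake.

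**Link to efficiency.** If the total recording period is T, then SE = TST / T, and WASO as written = T − TST = (1 − SE) × T. It is then fixed by TST and SE. The documents do not say that the recording period is T, so this step is conditional.

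**Illustration.** Assumed values, none from the documents: N = 3, S = 360, W = 45, with P varied and the recording period taken as T.

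| P | T | SL | SE | WASO as written | Wake after onset | Excess |
|---|---|---|---|---|---|---|
| 0 | 408 | 3 | 0.890 | 45 | 45 | 0 |
| 0.5 | 408.5 | 3.5 | 0.889 | 45.5 | 45 | 0.5 |
| 10 | 418 | 13 | 0.868 | 55 | 45 | 10 |
| 30 | 438 | 33 | 0.829 | 75 | 45 | 30 |
| 60 | 468 | 63 | 0.776 | 105 | 45 | 60 |

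Worked for P = 30: T = 30 + 3 + 360 + 45 = 438, TST = 363, and T − TST = 75. Wake after onset is 45, so the excess is 30.

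**Between groups.** If mean pre-onset wake were 30 minutes in insomnia and 10 in good sleepers, with W = 45 in both, the written rule gives 75 against 55. That is a 20-minute difference where wake after onset does not differ. In general the added difference equals the difference in mean P.

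**Where WASO is used.** The primary outcome is "Dementia biomarkers in cerebrospinal fluid" and the secondary is CSF orexin. The Analysis Plan compares CSF analytes and models group and orexin against the amyloid markers. The sample size under Accrual rests on the orexin and amyloid oligomer assays. Eligibility uses the diagnostic criteria, the Insomnia Severity Index, the apnea-hypopnea and limb movement indices, and actigraphic sleep duration. WASO appears in none of these.

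**The case against.** The strongest reply is that nothing in the study depends on WASO, and that stands: the variable is listed once, to be computed, and no test uses it. A reader might infer that the CSF findings or the definition of the insomnia group are compromised. The documents do not support that, because neither uses any value derived from this rule.

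Four other strong readings also fail.

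- *Every participant's value is wrong.* The excess is zero for anyone with no wake epoch before onset. Staff might also follow the variable's name rather than its rule; the documents do not settle which.
- *The group difference is exaggerated.* No comparison of WASO between groups is planned, and slow sleep onset is one of several alternative complaints. A larger excess in insomnia is plausible but not established.
- *Onset and maintenance problems can no longer be told apart.* SL is reported separately, and wake after onset can be recovered as WASO as written − SL + N. For P = 30 this is 75 − 33 + 3 = 45.
- *The minutes above are the size of the error.* They are assumed and only show that the excess equals pre-onset wake.

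One possible defence does not succeed. The reference to standard criteria concerns the scoring of epochs, whereas WASO is given its own explicit rule, and that rule contradicts its name.

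**Conclusion.** The definition is wrong as written: applied literally, it yields total wake time under the name WASO. The overstatement is exactly the wake time between lights out and sleep onset, at least 0.5 minutes in anyone with a wake epoch there. Its typical size cannot be stated, because the documents give no latencies. That the variable duplicates TST and SE rests on the assumption that the recording period runs from lights out to lights on. SL, TST and SE as defined are unaffected. This is a minor correction to a descriptive polysomnography variable, confined to any table or text that reports WASO.

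**What to change.** Redefine WASO as the minutes scored awake from sleep onset, meaning the first epoch of stage 2 or higher as already used for SL, to lights on. State that single end point. Stopping at the final awakening would be a different variable, because it drops wake between that awakening and lights on. If the lights-out-to-lights-on quantity is also wanted, report it as total wake time. It would help to say in the same sentence whether the total recording period is lights out to lights on.

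The cost is one sentence of text. The existing epoch scoring is sufficient, and any values already computed can be recomputed from it. No procedure, sample size or planned analysis changes.

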
the treatment of chronic insomnia.

Study Design

Phase* Not applicable

Design

Laboratory Observational study

Study duration

The total duration of the study will be 24 months, each participants duration in the study will be approximately 4 weeks.

Resources necessary for human research protection

Describe research staff and justify that the staff are adequate in number and qualifications to conduct the research. Describe how you will ensure that all staff assisting with the research are adequately informed about the protocol and their research related duties. Please allow adequate time for the researchers to conduct and complete the research. Please confirm that there are adequate facilities for the research.

The principal investigator involved in this project has extensive experience in sleep research, including having a history of success in conducting studies with CSF sampling. A study coordinator will be hired for this study and they will be trained in all designated duties and responsibilities of the study. [name] will provide oversight of the study coordinator. The study will be conducted at the CTRC, where there are sufficient facilities and resources available.

Characteristics of the Study Population

Target population

Fifteen adults age 30-60 with chronic insomnia and fifteen age- and gender-matched good sleepers.

Subjects enrolled by Penn Researchers 30

Subjects enrolled by Collaborating Researchers

0

Accrual

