At an initial visit, participants will provide informed consent; complete standard questionnaires on sleep, cognitive functioning, and demographics this visit, which will be completed remotely. All information will be collected via RedCAP. Participants will then complete an ambulatory sleep study at home to screen for the presence of sleep disordered breathing and to characterize their sleep architecture. There is the potential for the data from the ambulatory sleep study to reflect reactivity to the recording equipment (i.e. a first night effect) this will be minimized by conducting the studies at home. Individuals who have evidence of sleep disorders based on the first night recording will be excluded from further participation in the study. The criteria for defining sleep disorders will be an appea-hypopnea index greater than 15 events per hour for sleep appea or a periodic limb movement index greater than 15 events per hour for PLMS. They will wear a wrist actigraph for one week and these data will be used to objectively assess sleep/wake patterns to determine eligibility based on habitual sleep duration. The actigraphy is a wrist-worn device that measures body movements. It is lightweight (17.5 g) and is worn like a wristwatch. Data are downloaded onto a personal computer and customized software uses the movement values to infer when the individual was awake or asleep. The methodology is commonly used to record sleep/wake patterns over several days. These data will be used to determine the individuals habitual sleep duration. In past studies, insomnia has most consistently associated with negative health outcomes when it is associated with objective evidence of short sleep duration (6 hours). As such, participants with insomnia who do not demonstrate average sleep duration 6 hours on actigraphy will not be eligible for further participation in the study. Participants who continue to be eligible following home sleep monitoring will then be studied in the Sleep Center on 11 Gates at the Hospital of the University of Pennsylvania for an overnight study. They will be arrive to the Sleep Center at 7:00 pm and will sleep overnight, following their habitual bedtime and wakeup time determined from the home actigraphy. Sleep will be monitored overnight using polysomnography. Standard polysomnographic procedures will be used to record the EEG, EOG, EMG, and EKG using an ambulatory system. Electrode placements of FpZ, CZ, OZ will be placed according to the International 10/20 system. Two EOG electrodes will be placed, positioned 1 cm below and

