
The following documents are currently attached to this item:

There are no documents attached for this item.

Deception

Does your project use deception? Deception could be considered any direct misinformation presented to the subject or omission of key information pertaining to the design or nature of the project. No

International Research

Are you conducting research outside of the United States? No

Analysis Plan

Paired-samples t-tests will be conducted to compare each of the CSF analytes between patients with chronic insomnia and matched good sleepers. Multiple regression analyses will be used to examine whether CSF orexin levels mediate the relationship between chronic insomnia and AB markers. Mediation analyses will be conducted using a series of linear regression models in which group (insomnia or control) and orexin levels will be treated as independent variables and AB markers will be treated as the dependent variables.

The following documents are currently attached to this item:

There are no documents attached for this item.

Data confidentiality

- x Paper-based records will be kept in a secure location and only be accessible to personnel involved in the study.
- x Computer-based files will only be made available to personnel involved in the study through the use of access privileges and passwords.
- x Prior to access to any study-related information, personnel will be required to sign statements agreeing to protect the security and confidentiality of identifiable information.
- x Wherever feasible, identifiers will be removed from study-related information.

A Certificate of Confidentiality will be obtained, because the research could place the subject at risk of criminal or civil liability or cause damage to the subject's financial standing, employability, or liability.

A waiver of documentation of consent is being requested, because the only link between the subject and the study would be the consent document and the primary risk is a breach of confidentiality. (This is not an option for FDA-regulated research.)

Precautions are in place to ensure the data is secure by using passwords and encryption, because the research involves web-based surveys.

Audio and/or video recordings will be transcribed and then destroyed to eliminate audible identification of subjects.

Subject Confidentiality

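### With no margin over 15 per group, one missing CSF sample also removes the matched partner's sample from the Aim 1 paired t-test; a model that keeps unpaired samples avoids this

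*Combined protocol and SAP*

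**What the plan says.** The Target population entry gives "Fifteen adults age 30-60 with chronic insomnia and fifteen age- and gender-matched good sleepers", and the enrolment field reads "Subjects enrolled by Penn Researchers 30", with none from collaborators. The Accrual section concludes that "N=15/group would be sufficient to identify changes in the 8 AM samples" at 80% power, for differences of at least 30% in OxA and 100% in ABO. That calculation is described thus: "two-sided two-sample t-test was utilized for a two-group parallel design study".

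Under Procedures, consent comes at the initial visit, and people can leave at three later points:
- After the home recording: "Individuals who have evidence of sleep disorders based on the first night recording will be excluded from further participation in the study".
- After a week of actigraphy, under a sleep-duration rule that applies to the insomnia group only.
- On the morning of sampling: "If contraindications are found, the lumbar puncture will not be performed and the subject will be withdrawn from all further study procedures".

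Potential Study Risks adds that participants may withdraw at any time.

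The Analysis Plan states: "Paired-samples t-tests will be conducted to compare each of the CSF analytes between patients with chronic insomnia and matched good sleepers". It also specifies linear regressions of the AB markers on group and orexin, for the mediation question. The text supplied gives no loss allowance and no rule for a pair in which only one member has CSF.

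**The concern.** The planned number and the required number are the same, so any missing CSF sample takes the study below the figure on which its power statement rests. The choice of test makes each loss cost more than it needs to. A paired t-test works on within-pair differences, so when one member has no CSF there is no difference and the other member's value drops out of the Aim 1 comparison. That second person may already have had a lumbar puncture. What is at stake is some precision in the main comparison. There is also an analysis decision about broken pairs that would otherwise be made after the data are seen.

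**Working it through.** **Inputs.** From Accrual: 15 per group, 80% power, two-sided two-sample t-test, 30% (OxA, raw scale) and 100% (ABO, natural log scale). From the Analysis Plan: paired t-test. Not given: alpha (0.05 two-sided assumed), the SD, the within-pair correlation ρ and any loss rate.

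**1. The plan's own figure.** Without an SD, 15 per group cannot be reproduced independently, so I back-solved it. With 28 degrees of freedom and noncentrality d/√(2/15), 80% power requires d = 1.06. The implied SD is at most 30%/1.06 = 28% of the mean for OxA, and ln 2/1.06 = 0.693/1.06 = 0.65 on the log scale for ABO.

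**2. Power of the stated paired test at that d.** With n intact pairs the noncentrality is d√n/√(2(1−ρ)), with n−1 degrees of freedom. For n = 12 and ρ = 0 it is 1.06 × √12/√2 = 2.60, which gives 66%.

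| Intact pairs | ρ = 0 | ρ = 0.2 | ρ = 0.3 | ρ = 0.5 |
|---|---|---|---|---|
| 15 | 77% | 85% | 90% | 97% |
| 14 | 74% | 83% | 87% | 96% |
| 13 | 70% | 79% | 84% | 94% |
| 12 | 66% | 75% | 81% | 92% |
| 10 | 56% | 66% | 71% | 85% |

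**3. How often pairs break (illustration only).** Suppose 15 fixed pairs, independent loss with probability p per person, no replacement and no re-matching. Expected intact pairs are 15(1−p)². Expected samples without a partner are 30(1−p) − 30(1−p)². The chance that every pair survives is (1−p)³⁰.

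| p | Intact pairs | Samples without a partner | All 15 pairs intact |
|---|---|---|---|
| 5% | 13.5 | 1.4 | 21% |
| 10% | 12.2 | 2.7 | 4% |
| 20% | 9.6 | 4.8 | 0.1% |

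At p = 2% the chance of at least one broken pair is already 1 − 0.98³⁰ = 45%.

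**4. What keeping the unpaired samples returns.** With m intact pairs, the paired estimate has variance 2(1−ρ)σ²/m. Adding s₁ and s₂ unpaired samples, the information matrix for the two group means is m times the inverse of the pair correlation matrix plus diag(s₁, s₂), in units of 1/σ² and treating ρ as known.
- Take 12 pairs plus 3 unpaired samples in one group. At ρ = 0 the variance falls from 2/12 = 0.167 to 1/15 + 1/12 = 0.150, a 10% reduction. At ρ = 0.3 it falls from 0.117 to 0.109, a 7% reduction.
- Over ρ from 0 to 0.5, with the unpaired samples in one group or split between groups, the reduction is about 2–11% for 12 to 14 intact pairs and 8–20% for 10.
- At ρ = 0 a two-sample test on 15 versus 12 gives 75%, against 66% for 12 pairs. That is roughly the most that could be recovered there, and part of it comes from the extra degrees of freedom.

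**The case against.** A reader might infer that enrolment is capped at 30, that replacement is barred, and that the study therefore cannot deliver 15 per group. The documents do not support this. The 30 is an entry in a form field; nothing calls it a ceiling on consents or forbids replacement. The Abstract and Overall objectives describe the fifteen with insomnia and their controls as the people who have polysomnography and CSF sampling. Procedures presents the home recording as screening and the actigraphy as an eligibility check. On that reading the two home steps produce screen failures that never count towards the 30. This part of the objection stands. What remains are losses on the laboratory night or the morning after.

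A reader might also infer that the 80% power is missed once fewer than 15 pairs remain. That does not follow either. The 80% was calculated for a two-sample test; at correlation 0.3, 12 pairs still give 81%, and at correlation 0 even 15 pairs give 77%. Fifteen per group is also described as sufficient for both analytes over coarse effect steps, so 80% may be a floor for one or both.

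Nor are the partner samples wasted. They can enter the mediation regressions, in which group is a term, and the protocol provides for specimen banking. The pair-loss table assumes no re-matching; if the remaining members could be re-paired freely, expected pairs would be 13.8, 12.9 and 11.1 at 5%, 10% and 20% loss.

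The objection does not remove the core: the stated Aim 1 test cannot use a sample whose partner is missing, and planned numbers leave no slack to absorb that.

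**Conclusion.** The point holds in a limited form. Planned enrolment equals the required number, at least one route to a missing sample lies after all screening, and the paired t-test then drops a second sample from Aim 1. The size is conditional. With d = 1.06 and two-sided alpha 0.05 assumed, going from 15 to 12 intact pairs lowers power from 77% to 66% at correlation 0, from 85% to 75% at 0.2 and from 90% to 81% at 0.3. How many pairs would break is unknown, because no loss rate is given. The stated power is not shown to be missed; it is left unprotected against losses that a different model would partly absorb. This is a cheap improvement to the analysis and does not show that the design fails.

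**What to change.** In the Analysis Plan, replace the paired t-test for each CSF analyte with a linear mixed model. Use group as a fixed effect, matched pair as a random effect and small-sample degrees of freedom, with ABO on the natural log scale and OxA on the raw scale, as in the sizing. Every CSF sample then contributes. When all pairs are complete and the estimated within-pair correlation is not negative, the model gives the paired-test result, so nothing is given up in that case.

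The cost is slightly more analysis work and the assumption that, in broken pairs, the missing member's value is missing at random. The gain in precision is modest, as the working shows.

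As a clarification only, state in Accrual that 15 per group means participants with an 8 AM CSF sample. If 30 is meant as a ceiling on consents, restate the power for the number expected to provide CSF. Either is a sentence of text.
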